#### 11.2.2. Demography

- Age at date of onset of the first symptom, will be expressed in years in the study. This will be computed as the difference between the date of onset of the first symptom and the date of birth (only if the data is available).
- The percentages will be computed by using only available information. Only frequencies will be provided for unknown or missing or not applicable categories
- Any measurements omitted or non-evaluable for a particular subject or analysis will not be replaced. Therefore, subjects with omitted or non-evaluable measurements will be excluded from the analysis

**11.2.3. Case definition**

- Influenza is defined as any positive laboratory test from one or more of the clinical specimens [Guidelines for the epidemiological surveillance of influenza, 2012].

**11.2.4. Number of decimals displayed:**

The following decimal description from the decision rules will be used

Display Table	Parameters	Number of decimal digits
Demographic characteristics	Mean, median age	1
Demographic characteristics	SD (age)	1
All summaries	% of count, including LL & UL of CI	1

**12. ANNEX 2: SUMMARY ON ELIMINATION CODES**

Not Applicable

### 13. ANNEX 3: STUDY SPECIFIC MOCK TFL

The following drafted study specific mocks will be used for each country (Panama, El Salvador, Guatemala and Trinidad, Dominican Republic, etc.,)

The data display, title and footnote is for illustration purpose and will be adapted to the study specificity as indicated in the TFL TOC.

Some of these templates were copied from EPI-FLU-032 BOD MX DB (201075) study. Note that there may be few changes between the study specific SAP mock TFL and the final TFLs as editorial/minor changes do not require a SAP amendment

#### Template 1 Number of specimen samples by calendar year - <country> (Screened cohort)

[figure not shown]
	Total specimen samples received	Respiratory virus positive		Influenza virus positive		Influenza A positive		Influenza B positive	
Year	N	n	%	n	%	n	%	n	%
Jan-Dec 2010									
Jan-Dec 2011									
Jan-Dec 2012									
Jan-Dec 2013									
Jan-Dec 2014									
Jan-Dec 2015									
Jan-Dec 2016									
Total									

N = total number of specimen samples received

[figure not shown]
n = number of positive specimen in a given category

%=(n/N)\*100

**Figure 1 Distribution of influenza positive specimens among number of specimen samples tested by calendar year - <country> (Screened cohort)**

**Figure 2 Distribution of influenza types among number of specimen samples tested by calendar year - <country> (Screened cohort)**

**Template 2 Number of specimen samples by influenza season - <country> (Screened cohort)**

	Total specimen samples received	Respiratory virus positive		Influenza virus positive		Influenza A positive		Influenza B positive	
<Southern/northern hemisphere influenza season>	N	n	%	n	%	n	%	n	%
May– Oct 2010									
May– Oct 2011									
May– Oct 2012									
May– Oct 2013									
May– Oct 2014									
May– Oct 2015									
May– Oct 2016									
Total									

N = total number of specimen samples received

n = number of positive specimens in a given category

% =  $(n/N) \times 100$

**Figure 3 Distribution of influenza positive specimens among number of specimen samples tested by influenza season - <country> (Screened cohort)**

Refer to [Figure 1](#)

**Figure 4 Distribution of influenza types among number of specimen samples tested by influenza season - <country> (Screened cohort)**

Refer to [Figure 2](#)

**Template 3 Summary of demographic characteristics by influenza types -**  
**<country> (Total cohort)**

		Influenza A positive N=XX		Influenza B positive N=XX		Influenza virus positive N = XX	
Characteristics	Parameters or Categories	Value or n	%	Value or n	%	Value or n	%
Age [Years]	n		-		-		-
	Mean		-		-		-
	SD		-		-		-
	Median		-		-		-
	Minimum		-		-		-
	Maximum		-		-		-
	Missing		-		-		-
Age group [Years]	0-4						
	5-17						
	18-49						
	50-64						
	>=65						
	Missing		-		-		-
Gender	Female						
	Male						
Region	West						
	Central						
	Panama						
	Northeast						
Patient type	Outpatient						
	Hospitalized						

N = number of influenza positive specimens

n = number of specimen positive in a given category

% = n / Number of specimens with available results x 100

Value = value of the considered parameter

SD = Standard deviation

West: Boca del Toro, Chiriquí and Comarca Nobe Bugle

Central: Coclé, Herrera, Los Santos and Veraguas

Panamá: Panamá Este, Panamá Oeste, Panamá Metro and San Miguelito

Northeast: Colón, Darien and Kuna Yala

**Template 4 Summary of demographic characteristics by influenza A subtypes and B lineages - <country> (Total cohort)**

		Influenza A subtypes				Influenza B lineage			
		H1N1 N=XX		H3N2 N=XX		Victoria N=XX		Yamagata N=XX	
Characteristics	Parameters or Categories	Value or n	%	Value or n	%	Value or n	%	Value or n	%
Age [Years]	n		-		-				-
	Mean		-		-				-
	SD		-		-				-
	Median		-		-				-
	Minimum		-		-				-
	Maximum		-		-				-
	Missing		-		-				-
Age group [Years]	0-4								
	5-17								
	18-49								
	50-64								
	>=65								
	Missing		-		-				-
Gender	Female								
	Male								
Region	West								
	Central								
	Panama								
	Northeast								
Patient type	Outpatient								
	Hospitalized								

N = number of influenza positive specimens

n = number of specimen positive in a given category

% = n / Number of specimens with available results x 100

Value = value of the considered parameter

SD = Standard deviation

West: Boca del Toro, Chiriquí and Comarca Nobe Bugle

Central: Coclé, Herrera, Los Santos and Veraguas

Panamá: Panamá Este, Panamá Oeste, Panamá Metro and San Miguelito

Northeast: Colón, Darien and Kuna Yala

**Template 5 Distribution of influenza A cases by month and year - <country>  
(Total cohort)**

Month and year (date of onset of symptoms)	Influenza virus positive (N)	Influenza A positive (n)	Percentage (%)
Jan2010			
Feb2010			
Mar 2010			
Apr2010			
May2010			
Jun2010			
Jul2010			
Aug2010			
Sep2010			
Oct2010			
Nov2010			
Dec2010			
Jan2011			
Feb2011			
....			
Dec2016			

N = number of influenza positive specimens with available test results by month and year

n = number of influenza A positive specimen in a given category

% = (n / N) x 100

**Template 6 Distribution of influenza B cases by month and year - <country>  
(Total cohort)**

Refer to [Template 5](#)

**Template 7 Distribution of influenza A subtype H1N1 cases by month and year - <country> (Total cohort)**

Month and year (date of onset of symptoms)	Influenza virus positive (N)	Influenza A subtype H1N1 (n)	Percentage (%)
Jan2010			
Feb2010			
Mar 2010			
Apr2010			
May2010			
Jun2010			
Jul2010			
Aug2010			
Sep2010			
Oct2010			
Nov2010			
Dec2010			
Jan2011			
Feb2011			
....			
Dec2016			

N = number of influenza positive specimens with available test results by month and year

n = number of influenza A subtype H1N1 specimens in a given category

% = (n / N) x 100

**Template 8 Distribution of influenza A subtype H3N2 cases month and year - <country> (Total cohort)**

Refer to [Template 7](#)

**Template 9 Distribution of influenza B lineage Victoria cases by month and year - <country> (Total cohort)**

Month and year (date of onset of symptoms)	Influenza virus positive (N)	Influenza B lineage Victoria (n)	Percentage (%)
Jan2010			
Feb2010			
Mar 2010			
Apr2010			
May2010			
Jun2010			
Jul2010			
Aug2010			
Sep2010			
Oct2010			
Nov2010			
Dec2010			
Jan2011			
Feb2011			
....			
Dec2016			

N = number of influenza positive specimens with available test results by month and year

n = number of Influenza B lineage Victoria specimens in a given category

% = (n / N) x 100

**Template 10 Distribution of influenza B lineage Yamagata cases by month and year - <country> (Total cohort)**

Refer to [Template 9](#)

**Template 11 Summary of influenza types by age group - <country> (Total cohort)**

[figure not shown]
		0-4 N=XX			5-17 N=XX			... N=XX			Total N=XX		
Influenza type	Categories	n	%	95% CI		n	%	95% CI		n	%	95% CI	
				LL	UL			LL	UL			LL	UL
Influenza A	Positive												
	Negative												
	Missing/Unknown	-	-	-	-	-	-	-	-	-	-	-	-
Influenza B	Positive												
	Negative												
	Missing/Unknown	-	-	-	-	-	-	-	-	-	-	-	-
Influenza A and B	Both Positive												
	Both Negative												
	At least one positive												
	Missing/Unknown	-	-	-	-	-	-	-	-	-	-	-	-

N = number of influenza positive specimens by age group

n = number of specimens in a given category

% = n / Number of specimens with available results x 100

95%CI= exact confidence interval; LL=lower limit; UL=upper limit

**Figure 5 Distribution of influenza types by age group - <country> (Total cohort)**

**Template 12 Summary of influenza A subtypes by age group - <country> (Total cohort)**

[figure not shown]
		0-4 N=XX			5-17 N=XX			... N=XX			Total N=XX		
Influenza A sub-type	Categories	n	%	95% CI		n	%	95% CI		n	%	95% CI	
				LL	UL			LL	UL			LL	UL
H1N1	Positive												
	Negative												
	Missing/Unknown	-	-	-	-	-	-	-	-	-	-	-	-
H3N2	Positive												
	Negative												
	Missing/Unknown	-	-	-	-	-	-	-	-	-	-	-	-

N = number of influenza positive specimens by age group

n = number of specimens in a given category

% = n / Number of specimens with available results x 100

95%CI= exact confidence interval; LL=lower limit; UL=upper limit

**Figure 6 Distribution of influenza A sub types by age group - <country> (Total cohort)**

**Template 13 Summary of influenza B lineage by age group - <country> (Total cohort)**

[figure not shown]
Influenza B lineage	Categories	0-4 N=XX				5-17 N=XX				... N=XX				Total N=XX		
		n	%	95% CI		n	%	95% CI		n	%	95% CI		n	%	95% CI
				LL	UL			LL	UL			LL	UL			
Victoria	Positive															
	Negative															
	Missing/Unknown	-	-	-	-	-	-	-	-	-	-	-	-	-	-	-
Yamagata	Positive															
	Negative															
	Missing/Unknown	-	-	-	-	-	-	-	-	-	-	-	-	-	-	-

N = number of influenza positive specimens by age group

n = number of specimens in a given category

% = n / Number of specimens with available results x 100

95%CI= exact confidence interval; LL=lower limit; UL=upper limit

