#### 3.2. Secondary objectives

From January 2010 to December 2015, in each selected country:

- To describe clinical features and outcomes (clinical manifestations, duration of illness, complications) of seasonal Influenza A and B cases in (overall and by subtypes or lineages) different seasons.
- To describe the temporal and geographical distribution of seasonal influenza A and/or B (overall and by subtypes or lineages) cases within different seasons.
- To estimate the percentage of co-circulation of influenza B lineages (Yamagata and Victoria lineages) among the study population, by age categories and by region.
- To describe the mismatch between the B-strain included in the Trivalent Influenza Vaccines (TIV) and the circulating B strains in different seasons.

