## 6.3. Secondary objectives

### 6.3.1. Analysis of secondary objectives planned in the protocol

Seasonal influenza A and/or B cases will be described using frequency and percentages by temporal (calendar weeks/months) and geographical distributions (by country and by region within the country [if data is available]) within different influenza seasons (2010-2011, 2011-2012, 2012-2013, 2013-2014 and 2014-2015). Frequency and percentage for clinical features and outcomes (clinical manifestations, duration of illness, complications) experienced by influenza positive subjects will be tabulated by type of influenza (seasonal influenza A and/or B) in different seasons from 2010-2015. Frequency and percentage for influenza B lineages by age (<1, 1-4, 5-9, 10-14, 15-19, 20-24, 25-44, 45-49, 50-59, 60-64 and ≥ 65 years) and region will also be provided.

The characteristics of the influenza B-infection as observed in the database and the B strain included in the trivalent influenza vaccine will be assessed using frequency and percentage for each year. The proportion of matched B-strains and mis-matched B-strains will be estimated along with 95% CI.

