**Figure 9 Distribution of influenza A subtypes by region - <country> (Total cohort)**

**Template 16 Summary of influenza B lineage by region - <country> (Total cohort)**

		West N=XX		Central N=XX		Panama N=XX			Northeast N=XX			Total N=XX			
Influenza B lineage	Categories	n	%	N	%	95% CI		n	%	95% CI		n	%	95% CI	
						LL	UL			LL	UL			LL	UL
Victoria	Positive														
	Negative														
	Missing/Unknown	-	-	-	-	-	-	-	-	-	-	-	-	-	-
Yamagata	Positive														
	Negative														
	Missing/Unknown	-	-	-	-	-	-	-	-	-	-	-	-	-	-

N = number of influenza positive specimens by age group

n = number of specimens in a given category

% = n / Number of specimens with available results x 100

[figure not shown]
95%CI= exact confidence interval; LL=lower limit; UL=upper limit

West: Boca del Toro, Chiriquí and Comarca Nobe Bugle

Central: Coclé, Herrera, Los Santos and Veraguas

Panamá: Panamá Este, Panamá Oeste, Panamá Metro and San Miguelito

Northeast: Colón, Darién and Kuna Yala

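### B-lineage co-circulation by age and region is undefined and tabulated with all years pooled, so the tables cannot show whether both lineages shared a region or age group in the same season

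*SAP*

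**What the plan says.** **Objectives and endpoint.** The third secondary objective in SAP 3.2 is "To estimate the percentage of co-circulation of influenza B lineages (Yamagata and Victoria lineages) among the study population, by age categories and by region". The second is "To describe the temporal and geographical distribution of seasonal influenza A and/or B (overall and by subtypes or lineages) cases within different seasons". The matching endpoint in SAP 4.2 names B lineages by age and by region, without season.

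**Analysis text.** For the third objective, SAP 6.3.1 offers "Frequency and percentage for influenza B lineages by age" and region, with no season stratum. For the second, it describes cases geographically "by region within the country [if data is available]) within different influenza seasons". Neither 6.3.1 nor 6.3.2 says what a percentage of co-circulation is or how to compute it.

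**Outputs by age and region.** Template 13, "Summary of influenza B lineage by age group - <country> (Total cohort", has age-group columns plus a total. Template 16, "Summary of influenza B lineage by region - <country> (Total cohort", has region columns plus a total. Templates 14 (types) and 15 (A subtypes) use the same regional layout. No title among the 33 listed templates and 17 listed figures crosses age group or region with season.

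**Outputs over time.** At country level, both lineages appear by month and year (Templates 9 and 10), by calendar year and season (Templates 21 and 22), by season against the vaccine lineage (Template 23) and in Figures 15 to 17.

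**Denominators.** Template 13 states "N = number of influenza positive specimens by age group", gives each lineage a positive, a negative and a missing row, and takes percentages over specimens with a result available. Templates 15 and 16 are region tables but carry the same N footnote. Template 14 correctly refers to region.

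**Match and mismatch.** SAP 6.3.1 says "The proportion of matched B-strains and mis-matched B-strains will be estimated along with 95% CI". The mock Template 23 has no CI columns.

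**The concern.** Co-circulation is a statement about time and place: both lineages present together. A split pooled over up to seven calendar years (2010 to 2015 in the Protocol, 2016 added in SAP section 9) answers another question, namely the lineage mix over the whole period. If one lineage gave way to the other between years, every region and age group would still show two lineages in Templates 13 and 16.

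Protocol 1.3 places B-lineage co-circulation across seasons and links it, with vaccine mismatch, to the added value of a quadrivalent vaccine. A regional or age-specific percentage that reads as co-circulation, but reflects replacement, would feed that argument wrongly.

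The denominator adds a second problem. With N counted over all influenza positives and a negative row for each lineage, it is open whether an influenza A specimen is lineage-negative or has no lineage result. Two programmers could print different lineage percentages from the same data.

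**Working it through.** **1. Inputs.** Protocol 5.2, Table 2 (Panama, calendar years 2010 to 2014). Influenza positive: 207, 47, 276, 190, 140. Influenza B positive: 14, 0, 178, 0, 55. The Protocol's stated yearly range of 47 to 276 reproduces (2011 and 2012). Sums: 207+47+276+190+140 = 860 and 14+0+178+0+55 = 247. The readable text gives no lineage counts (the Appendix A figures are not shown), so the lineages below are assumed and all B is taken as typed. Intervals are Clopper-Pearson, as in SAP 11.1: lower limit = Beta quantile 0.025 with parameters (x, n−x+1); upper limit = Beta quantile 0.975 with parameters (x+1, n−x).

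**2. Two opposite patterns, one pooled result.**

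| Year | B | Replacement: Victoria/Yamagata | Minority share | Co-circulation: Victoria/Yamagata | Minority share |
|---|---|---|---|---|---|
| 2010 | 14 | 14/0 | 0% | 11/3 | 21.4% |
| 2012 | 178 | 178/0 | 0% | 138/40 | 22.5% |
| 2014 | 55 | 0/55 | 0% | 43/12 | 21.8% |
| Pooled | 247 | 192/55 | 22.3% | 192/55 | 22.3% |

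In both patterns the pooled Victoria share is 192/247 = 77.7% (72.0–82.8%) and the Yamagata share 55/247 = 22.3% (17.2–28.0%). Under replacement, the Victoria share by year is 14/14 (76.8–100%), 178/178 (97.9–100%) and 0/55 (0–6.5%). The same ambiguity applies inside any one age or region column.

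**3. What the country tables add.** Template 21 would print 14/0, 178/0 and 0/55 under replacement, and 11/3, 138/40 and 43/12 under co-circulation. It separates the two patterns for the country, but not for a region or age group.

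**4. Denominator.** In the same assumed case, the total column of Template 13 gives Victoria 192/247 = 77.7% if influenza A specimens are left out, and 192/860 = 22.3% if they are coded negative. (That this equals the Yamagata share after rounding is a coincidence.)

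**5. Sparsity of a season split.** Spreading Table 2 B positives evenly over five age groups gives 14/5 = 2.8, 178/5 = 35.6 and 55/5 = 11 per group. Over the four Panama regions it gives 14/4 = 3.5, 178/4 = 44.5 and 55/4 = 13.75. There are no B cases in 2011 or 2013. Exact intervals at about those sizes:

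| Typed B in cell | Near an even split | Upper limit if Victoria is absent |
|---|---|---|
| 36 (2012, age) | 18/36: 32.9–67.1% | 9.7% |
| 44 (2012, region) | 22/44: 34.6–65.4% | 8.0% |
| 14 (2014, region) | 7/14: 23.0–77.0% | 23.2% |
| 11 (2014, age) | 6/11: 23.4–83.3% | 28.5% |

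So 2012 and 2014 could support estimates, 2010 counts only.

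**The case against.** **Lineage over time is already planned.** This stands. A reader might infer that the SAP cannot tell co-circulation from replacement at all. It can at country level, through Templates 9, 10 and 21 to 23 and Figures 15 to 17, and SAP 6.3.2 commits to lineage by country and hemisphere season. The gap is confined to age and region.

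**Templates 13 and 16 deliver the endpoint as worded.** Also true: SAP 4.2 asks for lineages by age and by region only. A reader might infer that the plan breaks a promise for age within season. No section makes that promise; the case for it rests on what co-circulation means and on Protocol 1.3. For region, the promise comes from the second objective and 6.3.1, subject to data availability, and it covers types and A subtypes too. Templates 14 and 15 therefore share the gap.

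**The denominator is clear enough.** An influenza A specimen naturally has no lineage result, SAP 11.2.2 bases percentages on available information, and the titles of Templates 19 to 22 name the wider denominator where it is meant. That is the more natural reading, but the negative rows and the N footnote leave the other one open.

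**The Template 23 interval is covered.** Largely so. SAP 6.3.1 promises it and 11.1 gives the exact method, so a missing mock column does not show that it was dropped.

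**Mock tables are illustrative.** SAP Annex 3 says they will be adapted in a table list that is not among the documents. That list could close some gaps, but the SAP text does not require it to, and it gives no definition of co-circulation.

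**The added tables would be thin.** True. That argues for showing counts, not for pooling away the timing.

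**Conclusion.** The point holds for the by-age and by-region analysis, as a cheap improvement, with medium confidence. The percentage of co-circulation has no definition, and the only outputs split as the objective asks cannot separate two lineages sharing a season from one replacing the other. In the worked case, the same pooled 77.7% corresponds to a yearly minority share of either 0% or about 22%.

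That contrast shows what the layout can hide; it is not a finding about Panama. Only the B totals come from the Protocol, full lineage typing is assumed, and Table 2 covers calendar years for one country. The missing region-by-season layout is a mismatch between the SAP's own text and its listed outputs. The age-by-season split is a recommendation. The N footnotes and the Template 23 columns are tidying.

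**What to change.** - In SAP 6.3.2, define co-circulation as the Victoria and Yamagata shares among lineage-typed influenza B within a season.
- Keep Templates 13 and 16. Add season-stratified versions by age group and by region, with counts, shares and an exact CI for one pre-named lineage (for example the Victoria share), not for a minority lineage chosen after seeing the data.
- Print counts only below a pre-stated number of typed B specimens (for example 10, where 5/10 already gives 18.7–81.3%), and mark cells with no typed B as not estimable.
- Add the region-by-season layout for Templates 14 and 15, as 6.3.1 promises where data allow.
- State in Templates 13, 16 and 23 that the lineage denominator is lineage-typed influenza B, that influenza A specimens are outside it, and that untyped B is shown as a count. Leave Templates 19 to 22 as they are.
- Tidying: correct the N footnote of Templates 15 and 16 to refer to region, and show in Template 23 the 95% CI already promised.

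The cost is one definition, season-stratified versions of existing tables, footnotes and CI columns; no new data are needed. The downside is sparse cells. Panama's May to October season cannot hold more cases than the calendar year, and Protocol 6.5.3 collects lineage only where available, so real cells will be no larger than the even-spread averages above imply overall. Counts for 2015 and 2016 are not in the documents.

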**Figure 7 Distribution of influenza B lineage by age group - <country> (Total cohort)**

**Template 14 Summary of influenza types by region - <country> (Total cohort)**

		West N=XX			Central N=XX			Panama N=XX			Northeast N=XX			Total N=XX		
Influenza type	Categories	n	%	95% CI		n	%	95% CI		n	%	95% CI		n	%	95% CI
				LL	UL			LL	UL			LL	UL			
Influenza A	Positive															
	Negative															
	Missing/Unknown	-	-	-	-	-	-	-	-	-	-	-	-	-	-	-
Influenza B	Positive															
	Negative															
	Missing/Unknown	-	-	-	-	-	-	-	-	-	-	-	-	-	-	-
Influenza A and B	Both Positive															
	Both Negative															
	At least one positive															
	Missing/Unknown	-	-	-	-	-	-	-	-	-	-	-	-	-	-	-

N = number of influenza positive specimens by region

n = number of specimens in a given category

% = n / Number of specimens with available results x 100

[figure not shown]
95%CI= exact confidence interval; LL=lower limit; UL=upper limit

West: Boca del Toro, Chiriquí and Comarca Nobe Bugle

Central: Coclé, Herrera, Los Santos and Veraguas

Panamá: Panamá Este, Panamá Oeste, Panamá Metro and San Miguelito

Northeast: Colón, Darién and Kuna Yala

